#### 3.10.1 Adverse Events

AEs will be coded using the MedDRA dictionary (Version 20.1 or higher). Treatment-emergent AEs (TEAEs) are any AE occurring or worsening in severity after the first administration of study medication. All AEs (including SAEs) will be graded using the 5-point Common Terminology Criteria for Adverse Events (CTCAE) V4.03 scale (mild, moderate, severe, life-threatening, or death). Causality with tesevatinib will be classified as: definitely related; probably related; possibly related; unlikely related; or not related.

The investigator will further assess the relationship of AEs to tesevatinib or the underlying disease.

The number and percentage of patients who experienced at least one TEAE as well as the number and percentage of patients who experienced AEs of each specific SOC and PT will be presented. For the presentation of AE incidences, the SOCs and the PTs within each SOC will be presented by decreasing total frequency. Tabulation by maximum severity and relationship to tesevatinib will also be included by treatment group.

The TEAEs, Grade  $\geq$  3 TEAEs, SAEs, and TEAEs leading to dose modification/discontinuation will be summarized by treatment arm, SOC, and PT. These analyses will be repeated for events considered related (definitely related/probably related/possibly related) to tesevatinib.

Subject listings will be provided for SAEs, AEs resulting in study drug discontinuation and deaths.

Adverse events will also be presented in listings. Time to onset and duration of AEs will be included in listings, along with action taken and outcome.

## 3.10.2 Clinical Laboratory Evaluation

The summary statistics (including number, mean, standard deviation, median, minimum and maximum) of all laboratory variables and changes from baseline will be calculated for each visit or study assessment by treatment group. For parameters of white blood cell counts, neutrophils (absolute count), lymphocytes (absolute count), monocytes (absolute count), hemoglobin, platelets, ALP, ALT, aspartate aminotransaminase, gamma glutamyl transferase, total bilirubin, glomerular filtration rate, plots of mean/mean changes from baseline with the corresponding standard error will be displayed.

For shift tables, laboratory results will be classified using the CTCAE Version 4.03. All graded laboratory parameters will be summarized separately for hematology and biochemistry. Corresponding shift tables comparing baseline to the worst post-baseline grade within the treatment period will be provided.

#### 3.10.3 Vital Signs

Descriptive statistics for vital signs (weight, temperature, blood pressure, pulse rate, and respiratory rate) values and the change from baseline will be presented for each scheduled assessment time point.

#### 3.10.4 ECG

Descriptive statistics for ECG parameters (i.e., PR interval, QRS interval, and QTcF interval) at each time point with triplicate ECGs will be presented for the values and

change from baseline scores. (QTcF is the QT interval using Fridericia's correction which is calculated by  $QTcF = QT/RR^{1/3}$ .)

The number and percentage of subjects with observed QTcF values that satisfy the following conditions will be presented by treatment group and study visit and categorized as:  $\leq 450$  ms; > 450 to 480 ms; > 480 to 500 ms; and > 500 ms.

The number and percentage of subjects having change from baseline QTcF values that satisfy the following conditions will be presented by treatment group and study visit and categorized as:  $\leq 0$  ms; > 0 to  $\leq 30$  ms; > 30 to  $\leq 60$  ms; and > 60 ms.

#### 3.11 Pharmacokinetic and Pharmacodynamic Analysis

PK serum concentration and all biomarkers will be summarized at each collection time-point.

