# 6.3. Exploratory objectives

- To evaluate the plasma concentrations of tesevatinib in patients with and without systemic steroid treatment
- To evaluate the potential association of exploratory tissue and blood biomarkers with response to tesevatinib and with adverse events. These include EGFRvIII mutation and gene amplification and may include circulating tumor DNA
- To evaluate the correlation between patients with EGFRvIIIpos tumor and those patients with EGFR gene amplification
- To evaluate and compare EGFRvIIIpos expression and/or other tissue biomarkers potentially associated with response with tesevatinib, in paired primary and recurrent glioblastoma specimens from the same patient, when these are available

- To evaluate patient-reported outcomes of disease and treatment-related symptom severity and interference as measured by the MDASI-BT questionnaire
- To evaluate patient-reported outcomes of disease and treatment-related symptom severity and interference as measured by the MDASI-BT in the subgroup of patients with EGFRvIIIneg and EGFR gene amplificationneg tumors as compared to those in patients with EGFRvIIIpos and EGFR gene amplificationpos tumors

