# 10.3. Corticosteroid Dose

At the time of each disease assessment, the corticosteroid intake will be compared with corticosteroid intake at the time of the last disease assessment. The changes will be recorded as Increased, Unchanged, or Decreased. Increases or decreases in corticosteroid dose should be clinically justified.

Note: Increases in corticosteroid dose for reasons other than disease control do not need to be taken into consideration when making this comparison.

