## 12.1.15. Prior and Concomitant Medications

All concomitant medications will be recorded from the time the patient signs the informed consent form through 30 days after the last dose of study drug.

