## 13.4.5. Plasma Concentrations

Plasma samples for tesevatinib concentration analysis will be drawn predose of tesevatinib on Day 15 of Cycle 1; and predose of tesevatinib on Day 1 of every subsequent cycle (up to cycle 6). Due to the sparse number of time points data are summarized using descriptive statistics by time points, systemic steroid treatment and subgroup.

These data, pooled with data from other studies, may be analyzed in a population PK analysis using nonlinear mixed effects modeling.

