## 3.6 Prior and Concomitant Medications

## 3.6.1 Medications and procedures for GBM

- Prior radiotherapy
- Prior systemic therapy
- Corticosteroid use at baseline

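### SAP 3.11 drops, without declaring it, the protocol's breakdown of tesevatinib concentration by systemic steroid treatment and EGFR subgroup, so the SAP as written does not deliver the exploratory steroid objective

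*SAP*

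**What the plan says.** Protocol 6.3 lists as an exploratory objective: "To evaluate the plasma concentrations of tesevatinib in patients with and without systemic steroid treatment". The synopsis carries the same objective. Protocol 13.4.5 supplies the matching analysis: "Due to the sparse number of time points data are summarized using descriptive statistics by time points, systemic steroid treatment and subgroup". Protocol 13.4.1 defines the two subgroups, EGFRvIII-positive and EGFR-amplified, and also a plasma concentration analysis population.

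SAP 3.11 says only: "PK serum concentration and all biomarkers will be summarized at each collection time-point". SAP 2.1 lists no exploratory objectives, and SAP 3.2 has no concentration analysis population. Steroids enter the SAP once as a summary item, in 3.6.1, as "Corticosteroid use at baseline", with no link to concentration. SAP 3.1.2 says that methods depart from the protocol in the primary and secondary analyses where needed. It mentions no change to the pharmacokinetic or exploratory analyses.

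**The concern.** A summary by time point alone mixes patients on and off steroids, so it cannot show whether their exposure differs. The protocol's own text makes the question relevant. Section 9.3.3 names CYP3A4 as the main metabolic route and expects co-medication to matter. Section 9.3 bars strong CYP3A4 inhibitors and inducers but allows steroids. Section 5.2 reports that QTc prolongation rose with plasma concentration. The documents do not say in which direction, if any, steroids would shift exposure, and the objective exists to look at that.

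Two documents that disagree on a planned output also leave the programmer to choose between them. If the SAP is taken as the working specification, the comparison disappears without anyone having decided to remove it.

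**Working it through.** The documents attach no power, alpha or effect size to this objective, so the check is a comparison of texts plus a count of what is collected.

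**1. Planned breakdown**

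| Item | Protocol 13.4.5 | SAP 3.11 |
|---|---|---|
| By time point | yes | yes |
| By systemic steroid treatment | yes | absent |
| By subgroup | yes | absent |
| Matrix named | plasma | serum |

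No other SAP section restores the two missing factors.

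**2. Is the change declared?** No. SAP section 1 says that it follows the protocol, Amendment 4. SAP 3.1.2 confines its changes to primary and secondary analyses, and this objective is exploratory.

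**3. Concentration data.** Protocol 13.4.5: "Plasma samples for tesevatinib concentration analysis will be drawn predose of tesevatinib on Day 15 of Cycle 1", and then predose on Day 1 of each later cycle up to Cycle 6. Scheduled samples per patient: 1 (Cycle 1 Day 15) + 5 (Day 1 of Cycles 2 to 6) = 6.

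**4. Steroid data.** Two sources exist.
- Protocol 12.1.15: "All concomitant medications will be recorded from the time the patient signs the informed consent form through 30 days after the last dose". This record is continuous, so status on any sampling date can be derived from it.
- Protocol 10.3: "At the time of each disease assessment, the corticosteroid intake will be compared with corticosteroid intake at the time of the last disease assessment". In the protocol's Table 1 the corticosteroid item falls on Day 1 of Cycles 2, 3 and 5 within the sampling period. It therefore coincides with 3 of the 6 samples and misses Cycle 1 Day 15, Cycle 4 and Cycle 6.

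Baseline use, the only steroid summary in the SAP, would miss the changes during treatment that 10.3 is written to record. The concomitant medication record is the source that covers all six samples.

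**5. Cell sizes.** Cycle 6 Day 1 falls 5 × 28 = 140 days after the first dose, or 140 / 30.4 = about 4.6 months. The protocol's sample size section assumes a median PFS of 4.5 months, so roughly half of 40 patients, about 20, would still be progression-free. With the assumed subgroup shares in protocol Table 7:
- EGFRvIII-positive: 20 × 0.27 = about 5
- EGFR-amplified: 20 × 0.57 = about 11

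These counts come before any steroid split. They assume that patients stay on treatment until progression and that PFS does not differ by subgroup.

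**The case against.** The strongest reply is that nothing has been lost. Protocol 13.4.5 still prespecifies the breakdown, the SAP presents itself as implementing the protocol, and a short sentence that does not mention steroids does not revoke a planned analysis. Individual concentrations will be listed (protocol synopsis and 13.4). The SAP leaves its list of tables to a separate document, which may contain the breakdown. The samples also have other stated uses: population pharmacokinetics and exposure-response work (protocol 12.1.13).

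Much of this stands. A reader might infer that the objective cannot be answered, or that it has no analysis anywhere. The documents do not support either reading, because the protocol contains the analysis and the data are collected. A reader might also treat the comparison as the whole purpose of the sampling. It is the only listed objective on concentration, but not the only use of the samples.

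What does not stand is that the SAP can be left alone. A listing is not a summary by steroid status. The table list is not part of the documents and the SAP text commits it to nothing. Protocol section 13 leaves further statistical detail to the SAP, and here the SAP gives less than the protocol.

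The change from plasma to serum looks like a wording slip. It alters no analysis and adds no weight.

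**Conclusion.** The point holds as an undeclared discrepancy between protocol and SAP. Two of the three breakdown factors in protocol 13.4.5 are missing from SAP 3.11, and a pooled summary by time point does not address the steroid objective. The importance is low. The objective is exploratory and descriptive, nothing is powered for it, and the primary PFS-6 conclusion is untouched. The conclusion assumes that the word subgroup in 13.4.5 means the two EGFR subgroups of 13.4.1, and that the unseen table list does not already restore the breakdown.

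**What to change.** In SAP 3.11, restore the descriptive summary of predose plasma concentration at each time point by systemic steroid treatment and by EGFR subgroup, as in protocol 13.4.5, and change serum to plasma. Because cells will be small, give the two factors as separate breakdowns rather than crossing them, and show the number of samples in each cell.

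Define steroid status for each sample. Neither document does so. This review proposes systemic steroid use on the sampling date, yes or no, taken from the concomitant medication records. Topical steroids, which protocol 9.1.4.2 suggests for rash, should not count as systemic use.

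If the sponsor means to drop either breakdown, SAP 3.1.2 should say so and give the reason.

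The cost is a time-varying flag to derive and check, two added factors in the table (one of them made up of two overlapping markers), and sparse cells at later cycles. No new data are needed. The result stays descriptive.

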## 4 LIST OF TABLES, FIGURES, AND LISTINGS

List of tables, figures, and listings will be completed in a separate document.
